6. CONCOMITANT THERAPIES AND OTHER RESTRICTIONS

Concomitant Therapies 6.1.

The PI will instruct the patient to notify the study site about any new medical treatment that she/he takes during the study period. All concomitant medications, both permitted and nonpermitted, and significant non-drug therapies (eg, surgery, blood transfusions, and physical therapy) administered/conducted after the patient is enrolled in this study will be recorded in the source documents and eCRF. All concomitant medications, including all prescription and over-the-counter drugs, supplements, and intravenous medications and fluids, taken by or administered to the patient within 28 days before Day 1 should be recorded as well.

CONFIDENTIAL

6.1.1. **Permitted Concomitant Treatment**

Supportive therapy considered necessary for the patients' welfare may be given at the discretion of the PI. This includes, but is not limited to, analgesics, anticonvulsants, anti-emetics, antidiarrheal treatment, laxatives, opiates, and transfusion of blood products.

6.1.2. **Prohibited Concomitant Treatment**

Patients are not allowed to receive other anticancer therapy, including surgery; chemotherapy; radiation therapy; immunotherapy; investigational agents; cytotoxic, biologic, or hormone therapy; anticancer Chinese medicine; or herbal remedies \leq 14 days (or \leq 5 half-lives, if applicable, whichever is shorter) prior to first dose and during the study. Hormone replacement therapy is allowed. Bisphosphonate and denosumab use is permitted if the patient had already been receiving it at a stable dose > 28 days before enrollment.

The primary metabolic pathway for pamiparib involves the CYP3A isoform. Administration of strong/moderate inhibitors of CYP3A or strong CYP3A inducers is not allowed ≤ 10 days or ≤ 5 half-lives, whichever is shorter, prior to Day 1 until the EOT visit. Refer to the drugs/substances listed in Appendix 6 for a more complete list of medications that are not allowed or that need to be taken with caution.

6.2. Diet

While confined at the study site, patients will receive a standardized diet at scheduled time do not conflict with other study-related activities.	es that

Caffeine-containing foods and beverages will not be allowed from 36 hours before Check-in until discharge from the CRU (Part 1).

12 December 2018 Page 38 of 72 Consumption of alcohol will not be permitted from 36 hours prior to Check-in until the end of Part 1.

CONFIDENTIAL

6.3. **Smoking**

Patients will not be permitted to use tobacco-containing products while admitted to the CRU. Nicotine replacement therapy will be available on request to be used per the package insert.

6.4. Contraception

Females of childbearing potential, nonsterile males, and female partners of nonsterile male study patients must agree to practice highly effective methods of birth control for the duration of the study and for at least 6 months after the last dose of study drug. Nonsterile males must avoid sperm donation for the duration of the study and for at least 6 months after the last dose of study drug. See Appendix 8 for contraception guidelines.

7. STUDY ASSESSMENTS AND PROCEDURES

Every effort will be made to schedule and perform the procedures as closely as possible to the nominal time, giving consideration to appropriate posture conditions, practical restrictions, and the other procedures to be performed at the same timepoint.

In Part 1, the recommended order of priority for scheduling procedures around a timepoint is (in descending order of priority):

- Physical examinations
- ECOG
- Vital sign measurements
- ECGs
- Blood and urine samples for clinical laboratory evaluations
- Dosing
- Blood samples for PK assessments of pamiparib, total radioactivity, and metabolites
- Start and end of urine and fecal collections for PK assessments.

In Part 2, assessments will be conducted at study visits as in the Schedule of Assessments in Appendix 4.

Pharmacokinetic Assessments (Part 1 Only) 7.1.

7.1.1. Pharmacokinetic and Metabolite Blood Sample Collection and Processing

Blood samples will be collected by venipuncture or cannulation at the times indicated in the Schedule of Assessments in Appendix 4 for determination of pamiparib concentration, total

12 December 2018 Page 39 of 72 radioactivity, and metabolite profiling and identification. Procedures for collection, processing, and shipping of blood samples will be detailed in a separate document.

CONFIDENTIAL

Approximately 1 × 2 mL blood sample will be collected for total radioactivity in whole blood and approximately 1×6 mL blood sample will be collected for total radioactivity in plasma. Approximately 1 × 4 mL blood sample will be collected for pamiparib concentration in plasma. Approximately 1 × 10 mL blood sample will be collected for metabolite profiling and identification in plasma.

7.1.2. Pharmacokinetic, Total Radioactivity, and Metabolite Urine and Fecal **Collection and Processing**

Urine will be collected over the time intervals indicated in the Schedule of Assessments in Appendix 4 for determination of pamiparib concentration, total radioactivity, and metabolite profiling and identification. Procedures for collection, processing, and shipping of urine collections will be detailed in a separate document.

Feces will be collected over the time intervals indicated in the Schedule of Assessments in Appendix 4 for determination of total radioactivity, and, where possible, metabolite profiling and identification. If possible, a single baseline fecal sample will be collected between Check-in on Day -1 and dose administration on Day 1. Procedures for collection, processing, and shipping of fecal collections will be detailed in a separate document.

7.1.3. **Emesis Sample Collection**

For patients experiencing emesis within 4 hours following oral dosing, vomitus will be collected. If possible, vomitus from patients experiencing emesis after 4 hours postdose will be collected. All vomitus collected will be stored for possible analysis as deemed appropriate.

7.1.4. **Analytical Methodology**

Plasma and urine concentrations of pamiparib will be determined using a validated analytical procedure. Whole blood, plasma, urine, and feces total radioactivity will be determined with liquid scintillation counting. Profiling and identification of metabolites in plasma, urine, and, where possible, feces will be conducted using standard laboratory procedures. Specifics of the analytical methods will be provided in separate documents.

7.2. Safety and Tolerability Assessments (Parts 1 and 2)

7.2.1. **Adverse Events**

Adverse event definitions, assignment of severity and causality, and procedures for reporting SAEs are detailed in Section 8.

The condition of each patient will be monitored from the time of signing the ICF to final discharge from the study. Patients will be observed for any signs or symptoms and asked about

12 December 2018 Page 40 of 72 their condition by open questioning, such as "How have you been feeling since you were last asked?," at least once each day while resident at the study site and at each study visit. Patients will also be encouraged to spontaneously report AEs occurring at any other time during the study.

CONFIDENTIAL

Any AEs and remedial action required will be recorded in the patient's source data. The nature, time of onset, duration, and severity will be documented, together with a PI's (or designee's) opinion of the relationship to study drug.

Adverse events recorded during the course of the study will be followed up, where possible, until resolution. This will be completed at the PI's (or designee's) discretion.

7.2.2. **Clinical Laboratory Evaluations**

Blood and urine samples will be collected for clinical laboratory evaluations (including clinical chemistry, hematology, serology, and urinalysis) at the times indicated in the Schedule of Assessments in Appendix 4. Clinical laboratory evaluations are listed in Appendix 1.

For all female patients of childbearing potential, a pregnancy test will be performed at the times indicated in the Schedule of Assessments (Part 1 and Part 2) in Appendix 4. An FSH test will be performed at Screening to confirm postmenopausal status.

The PI (or designee) will perform a clinical assessment of all clinical laboratory data.

7.2.3. **Vital Signs**

Supine blood pressure, supine heart rate, and oral body temperature will be assessed at the times indicated in the Schedule of Assessments in Appendix 4. Vital signs will be performed at other times if judged to be clinically appropriate, if the ongoing review of the data suggests a more detailed assessment of vital signs is required. These data will be captured in the eCRF. In line with local CRU policies, vital signs will also be assessed at other timepoints but will not be documented unless determined to be of clinical relevance.

All measurements will be performed singly and repeated once if outside the relevant clinical reference range.

Patients must be supine for at least 5 minutes before blood pressure, heart rate, and temperature measurements. During the in-house period in Part 1, blood pressure, heart rate, and temperature measurements should be conducted in the morning.

7.2.4. 12-Lead Electrocardiogram

Resting 12-lead ECGs will be recorded after the patient has been supine and at rest for at least 5 minutes at the times indicated in the Schedule of Assessments in Appendix 4.

Single 12-lead ECGs will be repeated once if outside the clinical reference range.

12 December 2018 Page 41 of 72 In the case of an abnormality such as prolonged QT interval corrected for heart rate using Fridericia's formula > 500 msec or > 60 msec from the highest baseline or predose value, new arrhythmia, or other clinically significant finding, ECGs will be recorded in triplicate at least 2 minutes apart.

CONFIDENTIAL

Additional 12-lead ECGs may be performed at other times if judged to be clinically appropriate or if the ongoing review of the data suggests that a more detailed assessment of ECGs is required. The PI (or designee) will perform a clinical assessment of each 12-lead ECG.

7.2.5. **Physical Examination**

Complete and limited physical examinations will be performed at the timepoints specified in the Schedule of Assessments in Appendix 4. A complete physical examination includes a review of the following systems: head/neck/thyroid; eyes/ears/nose/throat; respiratory; cardiovascular; lymph nodes; abdomen; skin; musculoskeletal; and neurological. A limited physical examination includes an assessment of the patient's general appearance, skin, thorax/lungs, cardiovascular, and abdomen.

7.2.6. **Eastern Cooperative Oncology Group**

The ECOG performance status will be evaluated at the times indicated in the Schedule of Assessments in Appendix 4.

7.2.7. **Tumor Assessments**

Tumor imaging (CT or magnetic resonance imaging [MRI], with preference for CT) will be performed at Screening or Part 2 Pre-dose Visit and every 12 weeks (± 7 days) from the time of the Part 2 C1D1. At the PI's discretion, CT or MRI scans may be repeated at any time if PD is suspected.

A CT scan or MRI of the thorax, abdomen, and pelvis plus other relevant evaluations as appropriate will be performed to assess all known disease.

The same imaging technique should be used for each patient throughout the study.

7.3. **End-of-Treatment Visit**

The EOT visit should occur within 7 days after pamiparib has been permanently discontinued. Required assessments are listed in Appendix 4. A visit should be scheduled as soon as possible, but the EOT visit may occur later after discussion with the Medical Monitor for specific circumstances, such as prolonged hospitalization. The visit at which tumor assessments showed PD may be used as the EOT visit provided that all required assessments were performed. Tumor assessments do not have to be repeated if they were performed within 14 days of the EOT visit or at a prior response evaluation that documented PD. An ECG does not have to be repeated if it was performed within 14 days of the EOT visit.

12 December 2018 Page 42 of 72

7.4. **Follow-up Assessments**

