8 SAMPLE SIZE JUSTIFICATION

No formal statistical assessment of sample size has been conducted. The sample size chosen for this study is common in human radiolabeled studies and is considered sufficient to achieve the objectives of the study. Up to approximately 10 patients will be enrolled and studied in order that 4 patients complete Part 1 of the study.

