10.1.2 Repeat and Unscheduled Readings

Repeat readings occur when the original vital signs or ECG result requires confirmation. Repeat readings are labelled as 'Repeat' in the listings and replace the original readings in all summaries and changes from baseline presentations and calculations. Prior to dosing, all readings taken in addition to the original reading are defined as predose repeats. Postdose repeat readings are defined as readings collected within 15 minutes of the actual time of the original reading. Where results are taken in triplicate and repeated, the last 3 readings are used in all subsequent calculations.

With the exception of predose results described above, unscheduled readings for vital signs or ECGs are defined as readings collected >15 minutes from the actual time of the original reading. Where results are taken in triplicate, the original reading is defined as the first reading of the triplicate. All results not taken at a scheduled timepoint for other data types (eg, clinical laboratory parameters) are unscheduled. Unscheduled readings are labelled as 'Unscheduled' in the listings. Because unscheduled readings are not associated with any scheduled timepoint, they are excluded from all summaries (with the exception that they may be used as baseline, as stated in Section 10.1.1).

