10.5.7 Tumor Assessment

Tumor imaging (CT or magnetic resonance imaging [MRI], with preference for CT) will be performed.

Data will be listed for individual patients and overall tumor assessment data for each tumor assessment (response rates) will be presented in a frequency table.

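### As written, the SAP leaves scans prompted by suspected progression out of all summaries, so the tumor response table can undercount progressive disease

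*Protocol*

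**What the plan says.** **Scan schedule.** Protocol 7.2.7 sets a scan at Screening or the Part 2 predose visit and then "every 12 weeks (± 7 days) from the time of the Part 2 C1D1". It also gives the investigator discretion outside that schedule: "CT or MRI scans may be repeated at any time if PD is suspected".

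**Repeat and unscheduled results.** SAP 10.1.2 confines repeats to two data types: "Repeat readings occur when the original vital signs or ECG result requires confirmation". For everything else it says: "All results not taken at a scheduled timepoint for other data types (eg, clinical laboratory parameters) are unscheduled". The consequence follows: "Because unscheduled readings are not associated with any scheduled timepoint, they are excluded from all summaries". The one stated exception is use as a baseline value.

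**Tumor table.** SAP 10.5.7 lists tumor data by patient and adds that "overall tumor assessment data for each tumor assessment (response rates) will be presented in a frequency table". It says nothing about off-schedule scans.

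**What happens after PD.** PD is a reason to stop treatment (Protocol 3.1.2, SAP 6.2). Protocol 7.3 waives the EOT scan where PD has already been documented, and allows the visit that showed PD to serve as the EOT visit if all required assessments were done. SAP 10.1 rules out imputation of missing values.

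**The concern.** The extra scans are ordered because progression is suspected. A rule that drops off-schedule results from summaries does little harm to routine laboratory values, but here it removes results according to their likely outcome. Stable disease and response are seen mainly at the scheduled 12-week scans and stay in; progressions found in between can fall out. The response frequency table is the only tumor summary that the SAP plans, and few patients will be in it, so one or two lost progressions would visibly change its percentages. The direction is predictable: the table would look more favorable than the data in the listings.

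**Working it through.** The plan has no figure to reproduce on this point. The study is descriptive ("No formal statistical assessment of sample size has been conducted"). The check is a cross-reading of the two documents, followed by an illustration on assumed numbers.

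**Step 1: how an extra scan is classed.** Repeats cover vital signs and ECGs only, so a suspected-PD scan does not replace a scheduled one. SAP 10.1.2 then takes in all other data types, with laboratory data given only as an example. A scan outside the 12-week timepoints falls in that class.

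**Step 2: what follows.** Unscheduled results leave all summaries. SAP 10.5.7 does not lift this for tumor data.

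**Step 3: whether the PD comes back later.**
- Next scheduled scan: not expected, because treatment ends at PD.
- EOT scan: need not be repeated once PD is documented.
- Imputation or carrying forward: excluded by SAP 10.1.
- PD visit used as EOT visit: possible, but optional and conditional. The SAP does not say that an EOT scan enters the table.

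Only the last route can recover the result, and it is not assured.

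**Step 4: how much of the calendar is off schedule.** The interval is 12 × 7 = 84 days and the window is 7 + 1 + 7 = 15 days (for the first scan, days 77 to 91). Days outside a window: 84 − 15 = 69, and 69/84 = 82%. This is a share of calendar days, not the probability that a given PD is found off schedule.

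**Step 5: effect on the table (all inputs assumed).** Let n = 8 patients treated in Part 2, P = 4 with PD before week 12, r = 1 responder at week 12, and u = PDs found on an off-schedule scan and not recovered through the EOT visit. The week-12 table then shows:
- PD: (P − u)/n on all treated, or (P − u)/(n − u) on those scanned at week 12
- Response: r/n on all treated, or r/(n − u) on those scanned

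| u | PD, all treated | PD, scanned | Response, all treated | Response, scanned |
|---|---|---|---|---|
| 0 | 4/8 = 50% | 4/8 = 50% | 1/8 = 12.5% | 1/8 = 12.5% |
| 1 | 3/8 = 38% | 3/7 = 43% | 1/8 = 12.5% | 1/7 = 14% |
| 2 | 2/8 = 25% | 2/6 = 33% | 1/8 = 12.5% | 1/6 = 17% |
| 3 | 1/8 = 13% | 1/5 = 20% | 1/8 = 12.5% | 1/5 = 20% |

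The PD figure falls on either base. The response rate moves only when the base is patients scanned.

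A smaller assumed case: with 4 patients in Part 2 and 1 off-schedule PD, PD goes from 1/4 (25%) to 0/4 or 0/3 (0%). With 2 such patients it goes from 2/4 (50%) to 0/4 or 0/2 (0%).

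The SAP gives only part of the denominator. Section 9 defines a Part 2 Safety Population and 10.1 ties summaries to the relevant population, but 10.5.7 does not say whether percentages use all of those patients or only those with a scan at the assessment in question.

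**The case against.** The other side has several fair points.

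- **The exclusion may not be meant for scans.** SAP 10.1.1 glosses unscheduled readings as laboratory parameters, 10.5.4 invokes 10.1.2 for vital signs while 10.5.7 does not, and 10.5.7 refers to each tumor assessment without limiting it to scheduled ones. This reading is possible. It does not displace a rule that covers all other data types and all summaries, and two programmers could build different tables from the same text.
- **The layout is not visible.** SAP section 4 puts table detail in a separate shell document. An EOT row, an unscheduled row or a best-response row there could solve the problem. This stands as a limit on certainty.
- **The PD visit can become the EOT visit.** True under Protocol 7.3, and it will rescue some cases.
- **Little depends on the table.** Tumor response is not among the primary or secondary endpoints (Protocol 2.2.1 and 2.2.2), Part 2 exists to give continued access (Protocol 3.2), and enrollment is small: "Up to approximately 10 patients will be enrolled and studied in order that 4 patients complete Part 1 of the study". Listings keep every PD, the reason for stopping treatment is recorded in the eCRF, and disposition is summarized (SAP 10.2). This stands and sets the weight of the point.

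A reader might infer that off-schedule progressions are never counted, or that the response rate is inflated in any case. The documents support neither. The EOT route and the unseen shells leave room for some PDs to be tabulated, and on an all-treated base the response rate does not change.

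**Conclusion.** The gap is real on the text. Taken together, SAP 10.1.2 and 10.5.7 allow a PD found between scheduled scans to be left out of the planned response table, and nothing in either document assures that it returns. The PD count is then understated by the number of such cases not recovered through the EOT visit. The response rate is overstated only if percentages are taken on patients scanned.

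The size cannot be fixed from the documents, because they give no progression rate, no share of PDs found off schedule and no number expected in Part 2. The 8-patient and 4-patient figures are illustrations only. The conclusion assumes that 10.1.2 is applied as written and that the table shells do not override it. The consequence is modest and touches no listed endpoint, but the correction is cheap and worth making before database lock.

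**What to change.** In SAP 10.5.7:

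1. State that the exclusion of unscheduled results in 10.1.2 does not apply to tumor assessments.
2. Count scheduled, unscheduled and EOT scans in the frequency table. A simple way is a best-overall-response row, with PD as one of its categories, using all scans up to PD or the start of new anticancer therapy. That row shows PD only for patients with no better earlier result, so add the number of patients with PD on any scan.
3. Name all patients treated in Part 2 as the denominator, with those without a post-baseline scan shown separately.
4. Flag unscheduled scans in the listing.

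Assigning an off-schedule PD to the next 12-week assessment and carrying it forward would also keep it in the table, but it shifts the date of the event and sits awkwardly with the no-imputation rule in SAP 10.1. The best-response row avoids both.

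Cost: one or two SAP sentences, one derivation and a simple count from the same data, and a matching change to the table shell if needed. No new data and no extra scans are required. The table may look slightly less favorable.

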c. Follow-up visit: to occur within 7 days of Discharge (if on Day 7 or before), or final non-residential visit (if discharge criteria have not been met by Day 7). If the patient is discontinued from the study, a Follow-up visit should occur within 7 days after dosing, and subjects will attend a Safety Follow-up visit approximately 30 days after the last day of study drug administration or before initiation of new anticancer therapy, whichever occurs first. This visit may occur later than 7 days

12 December 2018 Page 63 of 72

after discussion with the Medical Monitor for specific circumstances, such as prolonged hospitalization. An ECG does not need to occur at the End-of-Treatment visit if one was performed within 14 days prior to the visit. This visit will count as the patient's End-of-Treatment visit.

CONFIDENTIAL

Protocol Reference: BGB-290-106

- d. **Demographics:** Date of birth, gender, ethnicity, and race must be recorded.
- e. Medical History/Current Medical Conditions: General and disease-specific medical history including a history of past and current medical conditions must be recorded at Screening.
- f. Follicle-stimulating hormone: conduced in postmenopausal females only.
- g. **Pregnancy test (in female patients of childbearing potential):** Performed in serum at Screening and in urine at all other times. A positive urine pregnancy test will be confirmed with a serum pregnancy test.
- h. PK sample timepoints:
 - Blood sampling for pamiparib concentration (plasma): Predose and 0.25, 0.5, 1, 1.5, 2, 2.5, 3, 6, 12, 24, 48, 72, 96, 120, and 144 hours postdose. If patient does not meet discharge criteria by Day 7, additional samples may be collected every 24 hours after Day 7.
 - Blood sampling for total radioactivity (plasma and whole blood): Predose and 0.25, 0.5, 1, 1.5, 2, 2.5, 3, 6, 12, 24, 48, 72, 96, 120, and 144 hours postdose. If patient does not meet discharge criteria by Day 7, additional samples may be collected every 24 hours after Day 7.
 - ³ **Blood sampling for metabolite analysis (plasma):** 0.5, 1, 2, 6, 12, 24, 48, 72, 96, 120, and 144 hours postdose.

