 - ⁴ Urine collection: Predose (within 1 hour prior to dosing [patients will be asked to empty their bladder immediately prior to administration of [¹⁴C]-pamiparib on Day 1]) and 0 to 4, 4 to 8, 8 to 12, 12 to 24, 24 to 48, 48 to 72, 72 to 96, 96 to 120, and 120 to 144 hours postdose. Complete daily urine output may be collected at home if ≥ 90% of the radioactivity dose is not recovered while the patient is in the CRU.
 - ⁵ **Fecal collection:** Predose (-12 to 0 hours) and 0 to 24, 24 to 48, 48 to 72, 72 to 96, 96 to 120, and 120 to 144 hours postdose. Complete daily fecal output may be collected at home if ≥ 90% of the radioactivity dose is not recovered while the patient is in the Clinical Research Unit.

For subjects who meet Discharge criteria and are discharged from the CRU prior to Day 7, blood, urine, and feces sampling for PK will cease.

- i. Vital signs: Blood pressure, heart rate, and temperature must be measured after the patient has been supine for at least 5 minutes at Screening and in the morning during the in-house period
- j. **ECG:** Single 12-lead ECGs will be repeated once if outside the clinical reference range. A single ECG will be recorded unless there is an abnormality such as prolonged QTc(F) > 500 msec or > 60 msec from the highest baseline or predose value, new arrhythmia, or other clinically significant finding, then ECGs will be recorded in triplicate at least 2 minutes apart. ECGs will be recorded after the patient has been supine for at least 5 minutes.
- k. Complete physical examination: A complete physical examination includes a review of the following systems: head/neck/thyroid; eyes/ears/nose/throat; respiratory; cardiovascular; lymph nodes; abdomen; skin; musculoskeletal; and neurological.
- 1. **Limited physical examination:** A limited physical examination includes assessment of general appearance and additional examination of symptomatic systems or those affected by the patient's disease.

12 December 2018 Page 64 of 72

Study Procedures	Cycles 1 and 2		Cycles 3+b			
Day of Cyclo	Predose Visit ^a	D1 ^c	D15	D1	End-of-	
Day of Cycle					treatment	Follow-up
Allowed time window (days)	≤ 7 days prior to Cycle 1 D1	±2	±2	±2	Visitd	Visit ^e
Body weight	X	X		X	X	
Pregnancy test f		X		X	X	
Study drug administration:					_	
Pamiparib (60 mg twice daily) ^g			X	X		
Assessments:				779	et.	se.
ECOG performance status		X		X	X	
Tumor assessments: CT or MRI scan ^h	X (12 week intervals ± 7 days)					

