Safety and tolerability:	e2 59	۵.	197		40. 40.	
Adverse event recording	X	X	X	X	X	X
Prior/concomitant medication	X	X	X	X	X	X
Clinical chemistry and hematology	X	X	X	X	X	X^1
Urinalysis	X	X			X	g
Vital signs ⁱ	X	X	X	X	X	
12-lead electrocardiogram ^j	X				X	
Limited physical examination ^k	X	X		X	X	X

CONFIDENTIAL

Protocol Reference: BGB-290-106

Abbreviations: CT = computed tomography; ECG = electrocardiogram; ECOG = Eastern Cooperative Oncology Group; MRI – magnetic resonance imaging; QTc(F) = QT interval corrected for heart rate using Fridericia's formula.

- a. **Predose visit:** The Follow-up visit for Part 1 may be used as the predose visit for Part 2 if it occurs ≤ 7 days prior to the start of pamiparib treatment in Part 2. In this event, assessments only need to be conducted once.
- b. Cycle 3+: Cycles will continue as long as the patient is experiencing clinical benefit, or until occurrence of progressive disease (PD), unacceptable toxicity, pregnancy, death, withdrawal of consent, lost to follow-up, major protocol violation which in the opinion of the Sponsor would have significant impact on the study or its outcome, start of new anticancer therapy, withdrawal by the PI, or study termination by Sponsor.
- c. Cycle 1, Day 1: Assessments will be conducted prior to first dosing in Part 2.
- d. End-of-treatment visit: To occur within 7 days after the last day of study drug administration. A visit should be scheduled as soon as possible, but may occur later after discussion with the Medical Monitor for specific circumstances, such as prolonged hospitalization. An ECG does not need to occur at the End-of-Treatment visit if one was performed within 14 days prior to the visit.

12 December 2018 Page 65 of 72

e. **Safety Follow-up visit:** Approximately 30 days after the last day of study drug administration or before initiation of new anticancer therapy, whichever occurs first; a safety follow-up will occur with the outlined safety assessments. If new anticancer therapy is initiated before this safety follow-up, a safety follow-up should be scheduled as soon as possible. Clinical laboratory evaluations are only required if the patient had an ongoing clinical laboratory abnormality at the previous visit that the Principal Investigator considered to be related to study drug. For patients who do not want to or cannot return to the clinic for the safety follow-up, the patient should be contacted by telephone for a review of adverse events.

CONFIDENTIAL

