10.1.1 Definition of Baseline and Change from Baseline

Baseline for each parameter is in each part defined as the last value measured prior to dosing for that part i.e. Baseline for Part 1 is to be the last value prior to dosing for Part 1 and for Part 2, last value prior to the 1st dose in Part 2, including repeat (vital signs and electrocardiograms [ECGs]) and unscheduled (clinical laboratory parameters) readings (see Section 10.1.2 for definitions of repeat and unscheduled readings). For ECGs taken in triplicate, baseline will be the mean of the last 3 values taken prior to dosing.

Mean change from baseline is the mean of all individual patient's change from baseline values. Each individual change from baseline will be calculated by subtracting the individual patient's baseline value from the value at the timepoint. The individual patient's change from baseline

Statistical Analysis Plan Covance Study: 8381180

values will be used to calculate the mean change from baseline using a SAS procedure such as Proc Univariate.

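### The end-of-treatment ECG waiver does not ask for a post-dose tracing, so a patient who stops within about two weeks of starting Part 2 can finish with no scheduled ECG after Part 2 dosing

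*Protocol*

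**What the plan says.** The waiver appears in three places. Protocol Section 7.3 says "An ECG does not have to be repeated if it was performed within 14 days of the EOT visit". Appendix 4 has a near-identical sentence in footnote c of the Part 1 schedule and footnote d of the Part 2 schedule: "An ECG does not need to occur at the End-of-Treatment visit if one was performed within 14 days prior to the visit". None of the three says that the earlier ECG must have been taken after a dose.

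The scheduled ECGs in Appendix 4 are:

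- Part 1: Screening, Day -1, Day 1 (no clock time given), Day 5 and the Part 1 Follow-up visit.
- Part 2: the Predose visit, timed "≤ 7 days prior to Cycle 1 D1", and the EOT visit. There is none at Day 1 or Day 15 of Cycles 1 and 2, at Day 1 of later cycles, or at the safety Follow-up.

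Footnote a of the Part 2 schedule adds that "The Follow-up visit for Part 1 may be used as the predose visit for Part 2", provided that it falls inside the 7-day window. On the EOT visit, Section 7.3 says "The EOT visit should occur within 7 days after pamiparib has been permanently discontinued", with later visits possible after discussion with the Medical Monitor. For Part 1, footnote c says "If the patient is discontinued from the study, a Follow-up visit should occur within 7 days after dosing" and counts that visit as the patient's EOT visit.

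SAP 10.1.1 defines the Part 2 baseline as the "last value prior to the 1st dose in Part 2". SAP 10.1.2 keeps unscheduled ECGs out of all summaries except as a possible baseline, SAP 10.1 imputes nothing, and SAP 10.5.5 summarizes ECG data by part.

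**The concern.** A waiver of this kind is meant to spare a patient a duplicate of a recent tracing. Here the scheduled Part 2 tracing that can stand in for the EOT ECG was taken before Part 2 treatment began, so it duplicates nothing.

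Twelve-lead ECG parameters are a named secondary safety endpoint (Protocol 2.2.2). The matching objective concerns safety and tolerability in the treatment phase (2.1.2), and the SAP gives Part 2 its own Safety Population. A patient whose EOT ECG is waived in this way is in that population with a baseline and no scheduled later value. An ECG obtained at the investigator's discretion would be listed but, as an unscheduled reading, would not enter the Part 2 summary. Whether the value is missing depends on how early the patient stopped, so the post-baseline Part 2 ECG data would lean towards patients who stayed on drug longer.

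**Working it through.** The plan states no figure to reproduce here, so the check is an enumeration of the visit windows.

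**Part 2 inputs**

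- p = days from the Predose ECG to C1D1: 0 to 7 (Appendix 4, Part 2 schedule).
- L = cycle day of the last dose.
- e = days from last dose to the EOT visit: 0 to 7 (Section 7.3; later visits are possible by agreement and are left out).
- Waiver limit: 14 days.

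**Formula.** Days from Predose ECG to EOT = p + (L - 1) + e. The waiver is met when this is at most 14. Equivalently, EOT falls no more than 14 - p days after C1D1: 14 days for p = 0 and 7 days for p = 7. The latest qualifying last dose is L = 15 - p - e:

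- p = 0, e = 0: C1D15
- p = 7, e = 0: C1D8
- p = 0, e = 7: C1D8
- p = 7, e = 7: C1D1

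There are 8 x 8 = 64 whole-day pairs (p, e). The number that meet the waiver, by day of last dose, is:

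| Last dose | Condition | Pairs meeting the waiver |
|---|---|---|
| C1D1 | p + e ≤ 14 | 64 of 64 |
| C1D8 | p + e ≤ 7 | 36 of 64 |
| C1D11 | p + e ≤ 4 | 15 of 64 |
| C1D15 | p + e ≤ 0 | 1 of 64 |
| C1D16 or later | none | 0 of 64 |

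These are counts of what the windows allow, not probabilities; the documents do not say how visits will be spread within them. Part 1 ECGs do not change the result, because a tracing earlier than the Predose one can qualify only where the Predose one already does.

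**Part 1.** A discontinuation visit held on time is at most 7 days after the Day 1 ECG and at most 1 + 7 = 8 days after the Day -1 ECG, taking Day -1 as the day before Day 1. Both are inside 14 days. For a patient who leaves before Day 5, the remaining scheduled ECGs are Screening, Day -1 and Day 1, plus the Follow-up tracing that the waiver allows to be skipped. Whether any of these is post-dose turns on the Day 1 ECG. Appendix 4 gives it no time. Section 7 places ECGs ahead of dosing in a recommended order of priority, which makes a predose tracing possible but does not establish it.

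**The case against.** A reader might infer that early stoppers leave the study with no ECG after drug at all. The documents do not support that for Part 2. Patients reach Part 2 only after the single 60 mg Part 1 dose and normally have ECGs after it, at Day 5, at the Part 1 Follow-up, or both. The Part 2 Predose ECG itself follows that dose. What is missing is an ECG after the start of twice-daily dosing. Part 1 tracings do not fill that gap, because the objective and the summaries treat Part 2 separately.

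Three other strong readings also fail:

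- That every Part 1 discontinuation loses its post-dose ECG. On-time visits all fall inside the 14 days, but patients who stayed to Day 5 already have a scheduled post-dose tracing.
- That the gap falls where acute toxicity is most likely. The documents do not show this. Early stopping also covers progression and withdrawn consent, many toxicities lead first to a dose hold (Section 5.5), and no patient in Phase 1B of the earlier study discontinued for an adverse event (Section 1.3). The QTcF rule in Table 3 calls for triplicate ECGs, so patients stopped under it have on-treatment tracings.
- That the SAP would carry a pre-dose ECG into the EOT summary. No SAP rule does so.

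Mitigating provisions also count. The waiver allows the ECG to be skipped but does not direct it, and Section 7.2.4 permits extra ECGs. Section 4.4 calls for efforts to complete discharge assessments in withdrawn patients. Patients discharged after early emesis (Section 3.1.1) first have discharge procedures and then attend Follow-up; those who may go on to Part 2 are not clearly covered by footnote c's waiver. These provisions lower the chance of a gap without closing it. Finally, no inferential analysis is planned, and SAP 10.5.5 summarizes ECG change from baseline only for Part 1, so the effect is confined to a small descriptive summary.

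**Conclusion.** The point holds as a narrow gap in a measurement rule. A Part 2 patient whose EOT visit falls within 14 - p days of C1D1 (7 to 14 days, last dose no later than C1D15) can have the EOT ECG waived on the strength of the Predose tracing. That patient then has no scheduled ECG after Part 2 dosing and contributes no post-baseline Part 2 ECG. In Part 1 the gap is conditional: it needs discontinuation before Day 5 and a predose Day 1 ECG.

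The result assumes that visits keep to their stated windows and that the Predose ECG is the last before the first Part 2 dose, which makes it the SAP baseline. The documents give no rate of early stopping, so frequency cannot be estimated; few patients should be affected. One patient is 10% of a group of 10 and 25% of a group of 4, which is a share and not a rate. The size of the Part 2 group is not stated. This is an inexpensive improvement and does not threaten the primary pharmacokinetic objectives.

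**What to change.** In Section 7.3 and in Appendix 4 footnotes c (Part 1) and d (Part 2), let the waiver be met only by an ECG recorded after the first dose of that part and within 14 days before the EOT visit. Use one wording in all three places: Section 7.3 now counts days around the visit, while the footnotes count days before it. In Part 1 a post-dose Day 5 ECG would still qualify, and a predose Day 1 ECG would not, so the unstated Day 1 time would no longer matter for this purpose.

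The cost is wording in one section and two footnotes, and the ECG already listed for the visit could not be skipped in the few patients who stop early. One limit remains: in Part 2 only an unscheduled on-treatment ECG could then meet the waiver, and SAP 10.1.2 would list that reading without summarizing it. The change secures a post-dose tracing for each patient who attends the EOT visit, but not always a value in the summary table.
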